**Developing an implementation strategy for post-concussion communication with  
low health literacy parents in the emergency department**

**NCT Number:** NCT04112914

**Document Date:** 4/29/2021

*Please note: Due to the smaller sample recruited we simplified our analytic plan to focus on primary outcomes and no subgroup comparisons.*

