randomized to either the education toolkit intervention condition or treatment-as-usual control condition in a 2:1 ratio. For participants in the control group (Aim 2 and those randomized to control group in Aim 3), there will be no change to the nature of provider communication with families about closed head injury/concussion. Data will be collected about the experience that family's have seeking care in the ED for their child's closed head injury. For both Aims 2 and 3, survey data will be collected from parents at three time points: at initial ED visit before discharge, one day post-visit, and at 2-week follow-up. As part of parent data collection for Aims 2 and 3, all parents will complete the 3-item Brief Health Literacy Screen at the first time point of survey data collection. Please see timeline (uploaded in "Other Attachments" for more information regarding the timing of Aims 2 and 3.

For Aim 3 participants randomized to the intervention group, the parent education toolkit finalized in Aim 1 will be delivered by the study team. Based on feedback from qualitative interviews in Aim 1, the toolkit will consist of brief education from a member of the ED study team at enrollment, followed by asynchronous phone-based follow-up (audio/ voice and/or text). Parents will receive automated daily educational messages related to how they can provide recovery support to their children during the 2-week study period. Automated messages will be delivered via Twilio, by turning on the "initiate survey as SMS conversation" feature in REDCap. Parents will also receive reminders to schedule a follow-up appointment, with an option to receive tailored support from research staff to help with scheduling. A more detailed description and content of each toolkit component can be found in "Aim 3 Parent Education Toolkit Content" uploaded in "Other Attachments".

All patient materials will be available in both English and Spanish. Certified translations will be uploaded prior to use.

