### 10.4. Power analysis:

**Aim 1:** This is a qualitative study and thus a power calculation is not appropriate.

**Aims 2 and 3:** With 200 participants per group (Aim 2 and Aim 3), we will have  $\geq 98\%$  power to detect a meaningful 20% difference in the proportion of parents receiving each specific component of the reach measure (Table 1), in Aim 2 vs. Aim 3 groups, after allowing for 10% attrition ( $\alpha=0.05$ ). For Health Literacy subgroup comparisons, we will have  $\geq 80\%$  power to detect a 20% difference, assuming 10% attrition.

**Aim 4:** This is an exploratory, primarily qualitative study and thus a power calculation is not appropriate.

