**Aims 2 and 3: Primary outcomes.** We will compare parenting behaviors (emotional support and instrumental support) at Time 3 between the two groups using chi-squared tests for each behavior and total proportion of behaviors. **Secondary outcomes.** For each group (control and intervention), the percentage of parents reporting receipt of specific discharge components will be calculated and compared. We will also compare rates across specific subgroups, including high vs. low health literacy parents and between parents who speak English at home vs. those who do not. These percentages will be compared across subgroups using chi-squared tests to assess statistical significance. We will also compare characteristics of subjects who (a) agree to participate vs. those who do not, and (b) participate throughout follow-up vs. any lost to follow-up. We will also conduct exploratory analyses of the mean change in parent cognitions related to concussion management (concussion management knowledge, parental anxiety, and behavioral self-efficacy) and child well-being scores (child PEDs-QL and PCSI) from Time 1 to Time 3, between the groups using t-tests, and plotting trajectories for each group. We will adjust analyses for child age, sex, baseline post-concussion symptoms/severity, as well as covariates not determined to be effect modifiers, if associated with outcome and distributions vary by treatment group. Missing data will be examined for patterns with covariates, sensitivity analyses used to assess impact of missing data on results and imputation used as appropriate to address missingness. **Parent experiences with enhanced education.** Survey data will be analyzed descriptively, with associations by insurance status, language, and gender assessed. For qualitative data, audio-recorded and transcribed interviews will be coded using a deductive content analytic approach using consensual qualitative research methods. First, two independent coders will review each interview transcript, applying codes from the CFIR, Communication Accommodation Theory, and USE-EBPI while remaining open to other emergent themes. They will then compare codes and agree on final codes using a process of deliberation and consensus.

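### The primary comparison is specified as chi-squared tests with no effect estimate or confidence interval, so a non-significant result could not be read as either 'no worthwhile effect' or 'not informative'

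*Combined protocol and SAP*

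**What the plan says.** Section 14.1 (Aims 2 and 3, primary outcomes) compares emotional and instrumental support behaviours at Time 3 "between the two groups using chi-squared tests for each behavior and total proportion of behaviors". Further on, the same paragraph says analyses will be adjusted for child age, sex, baseline symptoms or severity and some other covariates. It does not say by what model, or what estimate the model should produce. For the primary outcome it gives no risk difference, ratio or mean difference, no interval, and no statement on how to read a non-significant result.

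The only difference called meaningful is in section 10.4. The power there is for "a meaningful 20% difference in the proportion of parents receiving each specific component of the reach measure", compared "in Aim 2 vs. Aim 3 groups" and "after allowing for 10% attrition". Section 14.1 treats receipt of discharge components as a secondary outcome. No meaningful difference and no expected rate are given for parenting behaviours.

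The note on the title page says: "Due to the smaller sample recruited we simplified our analytic plan to focus on primary outcomes and no subgroup comparisons". It does not give the number recruited. Under sections 5.2 and 8.1, all Aim 2 families are controls, and Aim 3 families are "randomized to either the education toolkit intervention condition or treatment-as-usual control condition in a 2:1 ratio".

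**The concern.** A chi-squared test shows whether the data conflict with equal proportions. It does not show how large a difference the data still allow. In a large trial a non-significant result usually comes with a narrow interval, so little is lost. In a small one, the same p-value can go with an interval that runs from slight harm to a substantial benefit.

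The simplified plan rests on the primary outcomes, in a sample that the sponsor says fell short. If the result is non-significant, the plan supplies nothing that separates a toolkit that does not change behaviour from a study that could not tell. A reader deciding whether to drop, keep or retest the toolkit needs that distinction.

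The total raises a second problem. A chi-squared test on a total proportion of behaviours suggests pooling all behaviour items across parents. That counts several answers from one parent as independent observations.

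**Working it through.** **1. The plan's own power figure.** Inputs from section 10.4: 200 per cohort, 10% attrition (180 left), alpha 0.05. Assumptions: two-sided test, 20% read as absolute points, base rates varied because none is stated.

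Power = Φ[(|p1 − p2| − 1.96·s0)/s1], with s0 = √[p̄(1 − p̄)(1/n1 + 1/n2)] and s1 = √[p1(1 − p1)/n1 + p2(1 − p2)/n2].

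At 40% vs 60% with 180 per group: s0 = 0.0527, s1 = 0.0516, and (0.200 − 0.1033)/0.0516 = 1.87, so power is 96.9%. At 20% vs 40% it is 98.7%. With 200 per group and no attrition, 40% vs 60% gives 98.1%. The stated 98% or more is reproduced to within about 1 point in the least favourable case. It applies to reach components and to 180 vs 180.

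**2. The randomised comparison at planned size.** 200 × 2/3 ≈ 133 and 200 × 1/3 ≈ 67; times 0.9 gives 120 toolkit and 60 control. Same formula, 40% control vs 60% toolkit: s0 = 0.0789, s1 = 0.0775, and (0.200 − 0.1546)/0.0775 = 0.586, so power is 72%. At 2:1, it is 47% for 100 completers and 31% for 60.

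**3. What an interval would show at 120:60.** Take 72/120 (60%) vs 30/60 (50%), assumed rates. Uncorrected chi-squared = 1.63, p = 0.20. The Wilson limits are 0.511 to 0.683 (toolkit) and 0.377 to 0.623 (control). Newcombe's interval for the difference of 0.100 is then:

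- lower: 0.100 − √[(0.600 − 0.511)² + (0.623 − 0.500)²] = 0.100 − 0.152 = −0.052
- upper: 0.100 + √[(0.683 − 0.600)² + (0.500 − 0.377)²] = 0.100 + 0.148 = +0.248

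This is about −5 to +25 points.

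**4. The same rates at other sizes.** Section 14.1 does not define the two groups. The rows below assume that Aim 2 and Aim 3 controls are pooled; at full size that is 120 vs 180 + 60 = 240.

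| Toolkit : control | Counts | p | 95% CI (points) |
|---|---|---|---|
| 120 : 240 (planned, pooled) | 72/120 vs 120/240 | 0.073 | −0.9 to +20.4 |
| 60 : 120 (half, pooled) | 36/60 vs 60/120 | 0.205 | −5.4 to +24.4 |

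**5. General width.** Half-width = 1.96·√[p(1 − p)/n1 + p(1 − p)/n2] with rates near 50%. The last column uses 20 points purely as a ruler. It shows how often, with no true effect, the interval around a non-significant result still includes +20 (200,000 simulated trials per row).

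| Toolkit : control | Half-width (points) | Null results still allowing +20 |
|---|---|---|
| 180 : 180 | 10.3 | about 1% |
| 120 : 240 | 11.0 | about 3% |
| 120 : 60 | 15.5 | about 27% |
| 67 : 33 | 20.8 | about 54% |
| 40 : 20 | 26.8 | about 68% |

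The achieved number is not in the documents, so the last two rows are assumed sizes.

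**6. The total.** If k behaviours per parent are pooled and have within-parent correlation ρ, the variance is inflated by 1 + (k − 1)ρ, and the true two-sided error of a nominal 5% test is 2·[1 − Φ(1.96/√(1 + (k − 1)ρ))]. Neither k nor ρ is documented. For assumed k = 5, ρ = 0.1, the inflation is 1.4 and the error about 10%. For k = 10, ρ = 0.3, they are 3.7 and about 31%. Simulation over the same assumed range gave 9% to 32%.

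**The case against.** The best reply is that this is largely a matter of reporting. Chi-squared is a valid test for a single yes/no behaviour. If counts and denominators are published, anyone can compute a crude interval for each one. The promised covariate adjustment cannot be done with a plain chi-squared test, so some model is implied, and models normally give estimates. Asking for an estimate and interval could be said of many plans that name only a test.

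Much of that stands, and it limits the point to what is prespecified and how a null is read. It does not close the gap. No model, estimate or interval is named. Counts pooled over behaviours would not give a valid interval for the total, because they lose the link between items from one parent.

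Some stronger readings are tempting and are not supported:

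- That the plan would report a non-significant result as no difference. It is silent on interpretation; it states no such rule.
- That 20 points is the plan's meaningful difference for parenting behaviours. Section 10.4 ties it to reach components. Used as a no-effect margin, it would let the report dismiss an intervention when the interval still allowed a 19-point gain.
- That a non-significant result is likely even if the toolkit works. This depends on the true effect and the achieved number. At 60 vs 120, power for 40% vs 60% is 72%, so about 28% of such trials would be non-significant. For 50% vs 60%, power is only 24%. The documents fix neither input.
- That the problem comes only from under-recruitment. The 120:60 case shows it at planned size.

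**Conclusion.** The point holds as a gap in specification; the test for each single behaviour is not wrong. The primary outcome has no prespecified effect estimate or interval, so a null result could not be classified.

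Its size depends on which groups are compared and how many families were recruited. With planned numbers and pooled controls, the half-width is about 11 points and the loss is modest. For randomised Aim 3 families at planned size it is about 15 points, and the illustrative 10-point difference gives roughly −5 to +25. Below about 108 completers at 2:1, even an observed difference of zero would have an interval reaching 20 points in each direction.

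These figures assume rates near 50%; at rates near 80% the intervals are narrower (±16.7 instead of ±20.8 points for 100 completers). They also assume 10% attrition and, for the reduced sizes, sample numbers that the documents do not give. The false-positive range for the total depends further on reading that test as one on pooled items, and on the assumed number and correlation of the items.

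**What to change.** Amend the primary-outcome text in section 14.1 as follows.

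- For each behaviour, make the risk difference with a 95% confidence interval (Newcombe or Miettinen-Nurminen) the primary result, with the chi-squared p-value as a supplement.
- For the total, compute each parent's proportion of behaviours and report the between-group difference in means with a 95% interval. Drop the chi-squared test on pooled behaviours.
- State that non-significant results are interpreted from the interval and are not reported as no effect. Where the interval covers both zero and a benefit that would matter, call the result inconclusive.
- Do not take over the 20-point figure as a margin. Any margin for parenting behaviours needs its own justification. Since the title-page note suggests that recruitment is over, a margin set after data were seen must be disclosed as post hoc.
- State whether the covariate adjustment applies to these estimates and, if so, by which model.

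This needs no new data or recruitment, only plan wording and a few lines of code. The downside is that the report may have to say 'inconclusive'.

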### 5.4. Data to be collected, including long-term follow-up data:

**Aim 1:** The goal of the parent interview will be to (1) explore their experiences with communication in the ED following their child's concussion and (2) provide critical feedback on the content and design of the CDC ACE Care Plan. The Cultural Treatment Adaptation Framework, will provide the foundation for the open-ended question guide for parents, with questions about the handout focusing on: (1) language and semantics, (2) use of culturally relevant examples, and 3) preferences for material delivery. The goal of the healthcare provider interviews will be to review the CDC ACE Care Plan handout and the RED Toolkit, and provide feedback about (1) barriers and facilitators to implementation in the ED and (2) the type of support (e.g., materials, training) that they believe would be helpful for implementation. CFIR^24 will provide the foundation for the open-ended question guide for healthcare providers, with a focus on individual characteristics (e.g., provider knowledge and self-efficacy), implementation toolkit characteristics, and aspects of the inner setting (e.g., time pressures in the busy ED, compatibility with existing communication networks and tools such as the EHR system) that may constrain implementation success.

**Aims 2 and 3:** Survey data will be collected from up to 200 parents at three time points: at initial ED visit before discharge, one day post-visit, and at 2-week follow-up. **Primary outcome.** Our primary outcome will be parenting behaviors at 2 week follow-up (emotional support and instrumental support). **Secondary outcomes.** Parent surveys at initial ED visit before discharge, one day post-visit, and two-weeks post visit will assess parent cognitions related to concussion management and proximal cognitions (concussion management knowledge and self-efficacy), parental anxiety related to concussion management, youth outcomes (health-related quality of life, post-concussion symptoms), the nature of provider-parent communication in the ED (e.g., did the parent have an opportunity to ask questions?), and additional

covariates (demographics and environmental conditions). In Aim 3 only, the parent surveys at 2 weeks post-visit will also include questions about their experiences with receiving the education toolkit.

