**Parent Interviews** (Aim 3 only): Based on parents' responses to their experiences with the education toolkit, a purposive recruitment strategy will be used to invite by email 12 parents to participate in one-on-one qualitative interviews. Interview content will be based on the Consolidated Framework for Implementation Research and Communication Accommodation Theory, assessing their experiences implementing content of the intervention, and their affective experience engaging with educators. Following best practice guidance for eliciting qualitative data about implementation barriers and facilitators and communication experiences, the question guide will remain open ended so that interviewers can explore other themes raised by participants.

**Aim 4:** (1) Cognitive interviews: The goal of the cognitive interview will be to assess understanding of survey questions and receive feedback on survey content. Research assistants will talk through questions with parents and identify 1) if question wording is confusing or challenging in any way, and 2) if questions could be asked in a way that is easier to understand. (2) Online surveys: The surveys will primarily assess parent behaviors, knowledge, and self-efficacy related to concussion management in order to validate our survey tool. Additional covariates (such as demographic information, previously diagnosed concussion) will also be collected for the purpose of ensuring the survey tool is valid and reliable for the general population. Survey questions will come from a bank of potential questions, which can be found in the support document "Aim 2 Parent Survey Questions".

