**Aim 4:** (1) Cognitive interviews: Analysis will be conducted by reviewing parents' comments and responses to questions about the survey tool. We will explore if there are any emergent differences in understanding survey questions among groups of parents (low vs. high health literacy). Data analysis will occur on an ongoing basis, with emergent results iteratively informing adaptations to the question guide and the survey itself; (2) Online surveys: Survey responses will be reviewed with a focus on the psychometric properties of items and scales (e.g., how are responses distributed), with the plan to retain only items with adequate variability and normal or near-normal distribution. To limit redundancies in the final survey, we will conduct exploratory analyses to determine which survey questions are correlated. Finally, we will compare responses across key parent characteristics (e.g., age, gender, prior concussion) to determine whether psychometric properties are similar across groups.

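### The primary chi-squared test of total behaviours leaves its unit open: pooling correlated answers would exceed 5% type I error, and the valid readings lose power against one score per parent for a general shift

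*Combined protocol and SAP*

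**What the plan says.** Section 5.4 defines the endpoint: "Our primary outcome will be parenting behaviors at 2 week follow-up (emotional support and instrumental support"). Section 14.1 gives the whole primary analysis in one sentence, a comparison of the two groups at Time 3 "using chi-squared tests for each behavior and total proportion of behaviors". Neither section gives the number of behaviours, their coding, a cut-off, or the unit counted in the test of the total. For Aim 4, section 5.4 says that "Survey questions will come from a bank of potential questions" held in a support document that is not part of the public file.

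Later in the same paragraph, section 14.1 adds: "We will adjust analyses for child age, sex, baseline post-concussion symptoms/severity, as well as covariates not determined to be effect modifiers". The only tests it names for comparing groups are chi-squared tests and, for exploratory change scores, t-tests. No adjusted method is named, and the text does not say whether the sentence reaches the primary outcome.

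The cover note says that fewer participants were recruited than planned and that the analysis was simplified to focus on primary outcomes. The achieved number is not given.

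**The concern.** A chi-squared test needs counts of independent units. A proportion of behaviours done is a score between 0 and 1 for each parent, so something must be done to it before it fits a table. Three readings are open:

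- **Pooled answers.** All behaviours done over all behaviours asked, by group. Several answers from one parent then count as independent.
- **Unordered table.** Parents are cross-classified by group and number of behaviours done. The test ignores the order of the scores.
- **Cut-off.** Parents are classed as above or below a threshold. The test ignores distance from it.

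The first can break the 5% level. The other two hold it but can discard information. After the simplification this test carries the main result, so the choice should not be left until the data are in hand. The adjustment sentence adds a second open choice on the same outcome: whether the primary comparison is adjusted, and by what method.

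**Working it through.** **The plan's own figure.** Section 10.4 states at least 98% power for "a meaningful 20% difference in the proportion of parents receiving each specific component of the reach measure", with 200 per group, 10% attrition and alpha 0.05 (two-sided assumed). With 200 × 0.9 = 180 per group and 40% vs 60%, the null standard error is √(2 × 0.25/180) = 0.0527 and the alternative one is √(2 × 0.24/180) = 0.0516. Power is Φ((0.20 − 1.96 × 0.0527)/0.0516) = 96.9%. It is 97.5% at 50% vs 70% and 99.8% at 10% vs 30%. The figure is reproduced to within about a point, but it concerns the reach measure. No power is stated for the primary outcome.

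**Inputs.** Section 5.2 has the Aim 3 cohort "randomized to either the education toolkit intervention condition or treatment-as-usual control condition in a 2:1 ratio", and counts as controls both the Aim 2 cohort and the Aim 3 controls. After 10% attrition:

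- Intervention: 200 × 2/3 × 0.9 = 120.
- Randomised controls: 200 × 1/3 × 0.9 = 60.
- All controls: 180 + 60 = 240.

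Assumed, because the documents do not give them: k behaviours per parent (2, 5 or 10), within-parent correlation rho (0.05 to 0.3), yes/no coding, and 50% of behaviours done in the control group.

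**Step 1: type I error if answers are pooled.** The true variance exceeds the one assumed by the test by the design effect DE = 1 + (k − 1) × rho. The actual error is 2 × (1 − Φ(1.96/√DE)). For k = 10 and rho 0.3, DE = 1 + 9 × 0.3 = 3.7, 1.96/√3.7 = 1.019, and the error is 30.8%.

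| k | rho 0.05 | rho 0.1 | rho 0.3 |
|---|---|---|---|
| 2 | 5.6% | 6.2% | 8.6% |
| 5 | 7.4% | 9.8% | 18.6% |
| 10 | 10.4% | 15.5% | 30.8% |

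At rho 0 it is 5%. Beta-binomial simulation at 120 vs 60 agrees (5.9% at k = 2, rho 0.1; 10.0% at k = 5, rho 0.1; 31.9% at k = 10, rho 0.3).

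**Step 2: power of the valid readings.** The simulation used 20,000 trials per scenario and beta-binomial scores. Entries are power (%) for the unordered table / cut-off at 60% of items / Welch t-test on one score per parent. For k = 2 the cut-off means both behaviours. With no true difference, these three tests reject in 4.1% to 5.4% of trials.

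| Intervention vs control parents | Behaviours done (control vs intervention) | k=2, rho 0.1 | k=5, rho 0.1 | k=10, rho 0.3 |
|---|---|---|---|---|
| 120 vs 60 | 50% vs 60% | 32/30/40 | 41/52/66 | 23/40/54 |
| 120 vs 60 | 50% vs 70% | 89/87/93 | 98/98/100 | 86/94/99 |
| 60 vs 30 (assumed half size) | 50% vs 70% | 60/58/68 | 76/81/92 | 50/71/84 |

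With all controls (120 vs 240), every valid reading has about 99% power or more for 50% vs 70%. For 50% vs 60% with k = 10 and rho 0.3, power is 46/68/85.

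**Hand check of the score column.** One parent's proportion has variance p(1 − p) × DE/k. For k = 10 and rho 0.3 this is 0.25 × 0.37 = 0.0925 in control and 0.24 × 0.37 = 0.0888 in intervention. At 120 vs 60 the standard error is √(0.0888/120 + 0.0925/60) = 0.0478, and power is Φ(0.10/0.0478 − 1.96) = Φ(0.13), about 55%. At 120 vs 240 the standard error is 0.0335 and power is Φ(1.02), about 85%. Both match the simulation to within about a point.

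**Step 3: does the replacement hold its level?** Linear regression with HC3 standard errors and three covariates, over 4,000 trials, rejects in 3.9% to 4.9% of null trials at 120 vs 60 and in 4.7% to 5.0% at 60 vs 30.

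**The case against.** **Nothing says that answers will be pooled.** Where the plan states a unit, it is the parent: section 10.4 uses the proportion of parents, and the secondary outcomes in section 14.1 are percentages of parents. This stands. A reader might infer that the primary test is invalid as planned, but the documents do not support that. The inflation also needs positive correlation within a parent. That is to be expected when one parent reports several behaviours, but the documents do not quantify it.

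**The score is not always stronger.** In a constructed case (240 vs 120, k = 10, correlation 0.3) the intervention only moved parents from 6 or 7 behaviours to 8. The table had 78% power, a cut-off at 8 had 63%, and the t-test 10%. The loss shown above is for a general shift. Validity of the other readings also has conditions. The cut-off must be fixed in advance, and cells must not be sparse: an all-behaviours cut-off rejected in as few as 1.4% of null trials in one scenario.

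**Chi-squared methods are not wrong in themselves.** A chi-squared trend test on the per-parent score comes within about 2 points of the t-test, and stratified chi-squared tests can adjust. Neither is named. The fair criticism is that the adjusted method and its scope are unstated.

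**Two further inferences do not hold.** Under Aim 4, section 14.1 plans to "retain only items with adequate variability and normal or near-normal distribution", from which a reader might infer graded behaviour items. That rule covers an online pool that also includes belief and knowledge items, and does not fix the final format. A reader might also infer that the condition on further covariates, "if associated with outcome and distributions vary by treatment group", threatens the error rate. Under assumed p < 0.05 thresholds, type I error stayed at 4.7% to 5.0%, and fixing the extra covariate in advance added only 1 to 4 points of power.

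**Conclusion.** The gap is real: the test of the total is not defined well enough to know its error rate or its power. Under pooling with positive correlation, type I error is above 5%, from about 6% (k = 2, rho 0.1) to 31% (k = 10, rho 0.3) in the illustrations. Under the table or cut-off readings the level holds, and the cost is power against a general shift.

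That cost is negligible for 20 points with all planned controls. At 120 vs 60 it is small in most scenarios, though the table loses 13 points (86% vs 99%) at k = 10 and rho 0.3. It is material for a 10-point effect or at half the randomised size. No document names 10 points as a target, and the half size is an assumption standing in for the unreported smaller sample.

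All figures rest on assumed k, rho, coding and control rate. They show the range at stake and do not predict this trial's result. The plan should be changed, because the choice affects the main result and the remedy is cheap.

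**What to change.** Replace the chi-squared test of the total with text such as: *One Time 3 score is calculated per parent, the proportion of the listed behaviours done; the items and their coding are given here. The score is compared between groups by linear regression with robust (HC3) standard errors on group, child age, child sex and Time 1 post-concussion symptoms. The adjusted difference in means is reported with a 95% CI. Answers are not pooled across parents.*

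In addition:

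- State that the adjustment sentence covers the primary outcome.
- Name the total score as the primary test. Report emotional support, instrumental support and the individual behaviours (chi-squared) as supporting results.
- If Aim 2 controls are included, state separately how the calendar-time difference between cohorts is handled, since these covariates do not remove it.

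**Cost.** No new data are needed: section 5.4 already collects post-concussion symptoms and demographics. A model-based estimate replaces a simpler test. If outcomes have already been seen, label the change post hoc and show the planned chi-squared results beside it.
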